11.2 Assessment of the Primary Endpoint

The primary efficacy endpoint is the mean intraocular pressure in the porous plate group as compared to the silicone plate group at 12 months. The analysis will compare the changes of intraocular pressure after the surgical intervention in the porous plate group as compared to the silicone plate group. Baselines will be compared to check for statistically significant differences and, if needed, a change from baseline analysis will be performed. The statistical significance of the differences in intraocular pressure will be determined using two-tailed paired t-tests.

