Glaucoma drainage implants used in this study are the Ahmed Glaucoma Valve (New World Medical, Inc., Rancho Cucamonga, CA) Model FP7 (silicone plate, 184 mm² surface area) and Model M4 (porous polyethylene plate, 191 mm² surface area). Both the Model FP7 and Model M4 are Food and Drug Administration-approved for implantation in humans with intractable glaucoma. Both of these valves will be supplied free of charge by New World Medical Inc for use in this study. Each participating site will be responsible for obtaining FP7 and M4 valves from New World Medical. The valves will not be shipped to UVA and then distributed to participating sites.

The Model M4 plate is approximately the same size as the Model FP7 plate (191 mm² and 184 mm² surface area, respectively). However, the theoretical surface area of the M4 is much higher because of the porous nature of the material. The porous polyethylene material is formed by a proprietary process (Porex Corporation, Fairburn, GA). The porous plate material is high density polyethylene with a long history of use in surgical implants (MEDPOR Biomaterial implants). Average pore sizes are greater than 100 micro-meters and pore

volume is in the 50 percent range, with an interconnecting open pore structure that allows for tissue ingrowth.

3. Study Objective

To evaluate and compare the clinical outcomes after implantation of the porous plate (polyethylene) Ahmed Glaucoma Valve with the silicone plate Ahmed Glaucoma Valve in subjects with intractable glaucoma.

4. Study Hypothesis

Eyes undergoing implantation with the porous plate Ahmed Glaucoma Valve are less likely to develop an elevation of intraocular pressure during the post-operative period and subsequently will have lower intraocular pressure and possibly require fewer glaucoma medications as compared with the silicone plate Ahmed Glaucoma Valve.

5. Study Endpoints

All study endpoints refer to the selected study eye only and are measured from Baseline to 12 months post-operative in the porous plate Ahmed Glaucoma Valve group as compared to the silicone plate Ahmed Glaucoma Valve group.

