5.1 Primary Endpoint

The primary endpoint is the mean intraocular pressure in the porous plate group as compared to the silicone plate group at 12 months.

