7.1 Inclusion Criteria

- Male or female of any race ≥ 18 years ≤ 80 years of age.
- Diagnosis of intractable glaucoma in the study eye, with the exception of silicone oil endotamponade induced glaucoma, which has not responded to conventional medical and surgical therapy.
- Elevated intraocular pressure > 21 mmHg in the study eye. Two consecutive measurements using Goldmann Applanation Tonometry will be obtained and the mean of those two measurements will be considered the subject's baseline intraocular pressure.
- Subject is a candidate for surgery in the study eye with a glaucoma drainage device.
- Subject is willing and able to sign the informed consent.

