11.1 Sample Size Considerations

With a sample size of 40 in each group, the power of the study will be 0.8 (80%) to detect a 1.5 mmHg difference in intraocular pressure with a standard deviation of 3 mmHg. Investigators will screen and treat patients until the study is fully enrolled or the study is terminated. All subjects undergoing surgical intervention will be entered in the statistical analysis. Based on prior studies, failure to complete the 12 month post-operative period is not likely to exceed 10% of randomized subjects.

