11.3 Assessment of the Secondary Endpoints

This secondary endpoint is the mean number of anti-glaucoma medications and surgical success in the porous plate group as compared to the silicone plate group at 12 months. The baseline number of medications will be compared to check for statistically significant differences and, if needed, a change from baseline analysis will be performed. The statistical significance of the differences in the number of medications will be determined using two-tailed paired t-tests. The mean number of medications at individual time points will be compared in the two groups. Kaplan-Meier survival analysis will be performed for statistical analysis of success rates, with comparisons of groups using the log rank test. Complications will be compared using comparison of proportions (z) test.

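### Section 11.2 does not fix one primary analysis and lets a baseline significance test steer it; a single pre-specified ANCOVA on baseline IOP should replace it

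*Combined protocol and SAP*

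**What the plan says.** Section 5.1 defines the endpoint as a month-12 quantity: "The primary endpoint is the mean intraocular pressure in the porous plate group as compared to the silicone plate group at 12 months". Section 11.2 opens with the same definition. Its next sentence describes a different analysis, without any condition: "The analysis will compare the changes of intraocular pressure after the surgical intervention". The sentence after that makes a change analysis conditional: "Baselines will be compared to check for statistically significant differences and, if needed, a change from baseline analysis will be performed".

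Section 11.3 applies the same rule to the first secondary endpoint: "The baseline number of medications will be compared to check for statistically significant differences and, if needed, a change from baseline analysis will be performed".

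Section 5 opens by saying that all endpoints "are measured from Baseline to 12 months post-operative". Section 11.1 powers the study "to detect a 1.5 mmHg difference in intraocular pressure with a standard deviation of 3 mmHg" without saying whether that SD belongs to month-12 IOP or to change. Section 11.6 fixes the analysis population but not the model. No baseline-adjusted model appears anywhere, although Section 7.1 gives every subject a defined baseline value: "Two consecutive measurements using Goldmann Applanation Tonometry will be obtained and the mean of those two measurements" is the baseline IOP.

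**The concern.** The second and third sentences of 11.2 cannot both be the rule. If changes are always compared, a conditional change analysis is redundant; if the change analysis is conditional, changes are not always compared. Two analysts following the text faithfully could report different primary results. The trial is unmasked, and the condition for the change analysis is left to judgement.

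A baseline significance test is also a poor trigger. Under randomisation any baseline difference is due to chance, so at the 5% level the test fires in about 1 trial in 20. The change score then subtracts the whole baseline imbalance, whereas the imbalance carries through to month 12 only in proportion to the slope of month-12 IOP on baseline IOP. At stake are the power of the primary comparison and the credibility of the result in exactly the trials the rule is meant to protect.

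**Working it through.** **Inputs from the plan.** 40 per arm, difference 1.5 mmHg, SD 3 mmHg, stated power 80% (11.1); 1:1 allocation (11); two-tailed tests (11.2).

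**Assumptions, because the plan is silent.** Two-sided alpha 0.05; the SD of 3 is the month-12 SD (S); baseline SD (B) 3, 5 or 8; baseline to month-12 correlation (r) 0 to 0.7; tests between independent arms. The paired t-tests named in 11.2 are a separate problem.

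**Step 1: the plan's own figure.** The noncentrality is 1.5 / (3 × √(2/40)) = 1.5 / 0.671 = 2.24. Power by the noncentral t is 59.8%, not 80%. The stated power is therefore not reproduced on a two-sample, two-sided basis. That is a separate point, but 59.8% is the reference below.

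**Step 2: power under each reading.** The SD that enters the test is:
- month-12 comparison: S = 3
- change score: √(B² + S² − 2rBS)
- ANCOVA: S√(1 − r²)

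For example, with B = 8 and r = 0 the change SD is √73 = 8.54, giving power 12.1%. With B = 3 and r = 0.7 it is √5.4 = 2.32, giving 81.4%.

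| r | Month-12 | Change, B=3 | Change, B=5 | Change, B=8 | ANCOVA (simulated) |
|---|---|---|---|---|---|
| 0 | 59.8% | 34.5% | 20.6% | 12.1% | 58.8–60.0% |
| 0.3 | 59.8% | 46.3% | 26.3% | 13.9% | 63.1–63.4% |
| 0.5 | 59.8% | 59.8% | 33.0% | 15.7% | 71.5–72.1% |
| 0.7 | 59.8% | 81.4% | 45.1% | 18.4% | 86.5–87.1% |

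ANCOVA matches or beats both alternatives at every setting, within simulation error. It gains nothing at r = 0, 3–4 points at 0.3 and about 12 at 0.5.

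**Step 3: the test-then-switch reading, no device effect.** The rule is month-12 IOP unless baselines differ at p < 0.05, then change (40,000 simulated bivariate normal trials per setting). The four figures in each cell are for r = 0 / 0.3 / 0.5 / 0.7.

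| B | Overall type I error (%) | Change-score false positives when the rule fires (%) |
|---|---|---|
| 3 | 6.4 / 5.7 / 5.0 / 4.1 | 32.4 / 24.4 / 19.3 / 13.3 |
| 5 | 7.4 / 6.7 / 6.3 / 5.4 | 53.0 / 44.0 / 43.6 / 41.2 |
| 8 | 8.1 / 7.8 / 7.4 / 6.8 | 67.5 / 66.0 / 64.2 / 67.1 |

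ANCOVA error is 4.9–5.2% overall and 4.3–6.1% when the rule fires.

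**Step 4: why the change score misleads when the rule fires.** Let β = rS/B be the slope. Given a baseline imbalance d, the month-12 comparison is off by βd and the change score by (β − 1)d. The change score overcorrects whenever β < 1. It is further from the truth than month-12 IOP when β < 0.5, and closer when β > 0.5. A rough size for d when the test fires is B√(2/40) × 2.34, where 2.34 = φ(1.96)/0.025 is the mean of |Z| beyond 1.96:
- B = 3, r = 0.7: β = 0.7; spurious difference 0.671 × 2.34 × 0.3 = 0.47 mmHg
- B = 8, r = 0: β = 0; 1.789 × 2.34 = 4.2 mmHg

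The simulated range is 0.47–4.12 mmHg, against a target difference of 1.5. Averaged over all trials the bias is at most 0.006 mmHg, because imbalances fall either way.

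**Step 5: other readings and inputs.** If the analyst may report whichever of month-12 or change is significant, type I error is about 8–10%. With month-12 SD 6 and B of 5 or 8, test-then-switch gives 3.8–6.8% overall and 7–42% when it fires.

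**The case against.** The strongest reply is that the endpoint itself is settled: 5.1 and the first sentence of 11.2 agree on the month-12 mean. The wording at the start of Section 5 covers all endpoints, including surgical success, so it reads more naturally as an observation window than as a change score. That is fair, and the opening of Section 5 is weak evidence of conflict. The conflict inside 11.2 remains.

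Second, 11.2 does not say that the change analysis replaces the month-12 comparison; it may be supplementary. In that case the test-then-switch error rates do not apply. This stands too: those rates illustrate one natural reading. But a plan that leaves replacement or supplement open has not named its primary result.

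Third, even under test-then-switch the overall harm is modest, there is no average bias, and the highest conditional rates need a baseline SD well above the month-12 SD. Switching can even help: at baseline SD 3 and correlation 0.7, when the rule fires, month-12 IOP gives a false positive in 33% of trials and change in 13%. All true. It shows that neither fixed choice is safe across the plausible range, whereas ANCOVA estimates the slope instead of assuming 0 or 1.

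Fourth, the named trigger is a baseline comparison, which does not depend on outcomes, so the room for choosing after the fact is narrower than it first appears. It is not closed, because no threshold is given.

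Last, fixing the unadjusted month-12 comparison would also remove the ambiguity. It would, but with no allowance for chance imbalance, which 11.2 plainly wants, and with less power wherever the correlation is appreciable.

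**Conclusion.** The concern holds. That 11.2 does not name one primary analysis follows from the text alone and needs no assumption; nothing elsewhere resolves it, and 11.3 repeats the rule.

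The size of the consequence rests on assumed baseline SD, correlation and alpha. On those assumptions the choice of reading moves power between 12% and 81%. Test-then-switch costs little on average but is unreliable in the roughly 1 trial in 20 where it acts. ANCOVA holds its error in those trials as well as overall.

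This is a change that should be made, not a fatal flaw. ANCOVA does not by itself restore the stated 80% power: if 3 mmHg is the month-12 SD, 40 per arm would need 1 − r² = 40/63 approximately, that is r of about 0.60.

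**What to change.** In 11.2, delete the sentence on comparing changes and the baseline significance test as a decision rule. Pre-specify one primary analysis: ANCOVA of month-12 IOP on arm with baseline IOP (the mean of the two readings in 7.1) as covariate, reporting the adjusted mean difference and its 95% CI. This also takes the place of the paired t-test. State that the month-12 value is likewise the mean of its two readings, since 8.3 requires two but does not say how they are combined. Handling of missing month-12 values needs its own rule. Add site as a factor only if randomisation was blocked by site.

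In 11.3, use the corresponding model for number of medications with baseline count as covariate, plus a check suited to a small count, such as a permutation test of the adjusted difference. In simulations with assumed counts of 0–5, ANCOVA type I error was 4.9–5.2%. Keep baseline tables descriptive. Settle all this before outcomes are compared by arm.

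The cost is wording and one degree of freedom; no new data are needed. If site is added, it takes one further degree of freedom per site beyond the first. The cap of 40 per site implies at least two sites for 80 subjects and at least three for 84–88. With three sites, power at correlation 0.3 goes from 63.9% (77 df) to 63.8% (75 df).

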All ophthalmic tests and examinations are for the selected study eye only.

If the subject satisfies all inclusion and exclusion criteria, the subject will be enrolled into the study.

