10.7 Aggregate Review of Adverse Events

The Medical Monitor will be responsible for the continuous review of unanticipated adverse events.

11. Statistical Considerations

This prospective, two-arm, unmasked, randomized, controlled trial will evaluate and compare the clinical outcomes after implantation of the porous plate (polyethylene) Ahmed Glaucoma Valve (M4) with the silicone plate Ahmed Glaucoma Valve (FP7) in patients with intractable glaucoma. Subjects will be randomized in a 1:1 ratio to one of two surgical intervention arms - surgical intervention with the Model FP7, Silicone Plate Ahmed Glaucoma Valve (Group A) or the Model M4, Porous Plate Ahmed Glaucoma Valve (Group B). The computer-generated randomization scheme (using varying block sizes of 2 to 4) will be completed by a staff member of the University of Virginia, Department of Ophthalmology, whose sole role in this study is to generate the randomization scheme. The subject surgical intervention arm assignment will be placed in a sealed envelope, securely delivered to the sites, and will be accessed by the site study staff in the site Surgical Admission Suite immediately prior to local anesthesia injection for the surgical procedure. Post-randomization, the assigned surgical intervention arm will be unmasked to the subject.

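### Paired t-tests are named for intraocular pressure and medication count, but the two arms are independent subjects, so no usable between-arm test is specified

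*Combined protocol and SAP*

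**What the plan says.** Section 5.1 and the opening of Section 11.2 define the primary endpoint as a comparison of mean intraocular pressure (IOP) between the porous and silicone plate groups at 12 months. Section 11.2 adds: "The analysis will compare the changes of intraocular pressure after the surgical intervention in the porous plate group", again relative to the silicone group. It then names one test: "The statistical significance of the differences in intraocular pressure will be determined using two-tailed paired t-tests".

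Section 11.3 uses parallel wording for the medication count: "The statistical significance of the differences in the number of medications will be determined using two-tailed paired t-tests".

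The design is a parallel-group one. Section 11 states: "Subjects will be randomized in a 1:1 ratio to one of two surgical intervention arms", using varying blocks of 2 to 4. Section 5 states: "All study endpoints refer to the selected study eye only", and Section 8.1 says the same of the examinations: "All ophthalmic tests and examinations are for the selected study eye only". No matching of subjects, crossover or fellow-eye comparison is described.

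Tests that suit independent groups appear only in Section 11.3, for surgical success (log-rank) and complications (z test of proportions). None is named for IOP or for medications.

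**The concern.** A paired t-test works on within-pair differences, so each observation in one arm needs a defined partner. Here the arms hold different people with one eye each, and blocked randomisation does not create matched pairs. The named test therefore cannot be applied to the stated contrast without an extra rule that the plan lacks.

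Two analysts following Section 11.2 could do quite different things. One might pair subjects across arms by some rule of their own. Another might run baseline against month 12 within each arm, where pairing is legitimate, but that answers whether pressure fell and not which valve is better. A third might take the word as a slip and run an independent-samples test. In an unmasked trial the primary test should not be left to such a choice, and the medication endpoint has the same problem.

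**Working it through.** **Inputs.** From Section 11.1: 40 per group, difference 1.5 mmHg, SD 3 mmHg, stated power 80%, and on dropout, "failure to complete the 12 month post-operative period is not likely to exceed 10% of randomized subjects". The documents give no alpha, so two-sided 0.05 is assumed throughout. They also do not say which quantity the SD describes.

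**1. Does the stated power show which test was meant?** Noncentral t, 40 per arm:

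| Test | Standard error (mmHg) | Noncentrality | df | Power |
|---|---|---|---|---|
| Independent groups | 3 × √(2/40) = 0.671 | 1.5/0.671 = 2.236 | 78 | 0.598 |
| Arbitrary pairs (SD of differences 3√2 = 4.24) | 4.24/√40 = 0.671 | 2.236 | 39 | 0.587 |
| Paired, 3 mmHg read as the SD of differences | 3/√40 = 0.474 | 1.5/0.474 = 3.162 | 39 | 0.869 |

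None gives 0.80. A paired test with SD 3 in each arm reaches 0.80 only at a within-pair correlation of about 0.39, and this design has no pairs. Section 11.1 therefore does not settle the reading.

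**2. Reading across arms.** The second row shows the average cost: the same standard error with 39 degrees of freedom in place of 78, and about one point of power. In simulation (200,000 trials, pairing blind to outcome) the type I error is 0.050. What changes is whether the answer is reproducible. Two outcome-blind pairings of the same data disagree on p < 0.05 in 2.0% of trials at no true difference, 4.9% at 0.75 mmHg and 7.0% at 1.5 mmHg.

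The disagreement is concentrated near the significance boundary. With both arm SDs set to 3, over 20 data sets of 5,000 pairings each:

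| Observed difference (mmHg) | Independent-test p | Share of pairings with p < 0.05 |
|---|---|---|
| 0.5 | 0.458 | 0% |
| 1.0 | 0.140 | 0.2% |
| 1.3 | 0.056 | 31% |
| 1.5 | 0.028 | 92% |
| 1.9 | 0.006 | 100% |

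**3. Unequal arms.** Pairing also needs equal numbers. Take completers in each arm as independent binomials with n = 40. The chance that the counts differ is 1 − Σ P(k)², summed over the possible completer counts k. This is 0.79 at 5% dropout (mean gap 1.5 subjects) and 0.85 at 10% (mean gap 2.1). In most trials a completer analysis by pairs would have to drop someone.

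**4. Reading within arm.** Section 7.1 requires a baseline IOP above 21 mmHg, and the operation is meant to lower it. As an illustration, assume a fall of 2 to 3 mmHg and an SD of change of 4.24 (SD 3 at each time, no correlation). Neither figure is in the documents. The noncentrality is 2/0.671 = 2.98 to 3/0.671 = 4.47 on 39 df, so each arm's test is significant with probability 0.83 to 0.99, whichever valve is better. Two such p-values are not a between-arm test.

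**The case against.** The strongest reply is that this is a one-word slip with little numerical consequence. Section 11.2 states a between-group contrast before naming the test, and Section 11.1 speaks of 40 in each group, so most statisticians would run an independent test. Type I error is intact and the power loss is about one point. Inventing pairs is also an unlikely thing to do. If it were done, the fairer comparison is arbitrary pairing against the independent test, where verdicts differ in about 1.4% of trials at no difference and about 5% at 1.5 mmHg, less than the pairing-against-pairing figures.

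Much of this is fair. The slip is plausible and the average numerical harm is small. The within-arm figures rest on assumed inputs, and that argument stands without them. Loss of subjects arises only if pairing is combined with a completer analysis, whereas Sections 11.1 and 11.6 include everyone who has surgery. The unequal-arm figures also take exactly 40 per arm, although Section 11.4 allows up to 84 treated. The power shortfall is a separate matter and adds no weight here.

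What the reply does not remove is that the same test is named in two sections and nothing elsewhere corrects it. If everyone would in practice run an independent test, the correct analysis departs from the written plan, and the plan should be changed to match.

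**Conclusion.** The concern holds, and the text must be corrected before the analysis. The test named for the primary endpoint, and for the medication endpoint, does not fit a design of independent subjects, and no other between-arm test is given for either. Surgical success and complications are not affected.

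The size should be stated with care. This is a failure of specification and reproducibility, not inflated type I error. At 40 per arm, SD 3 mmHg and an assumed two-sided alpha of 0.05, an arbitrary pairing decides the outcome only when the result lies near p = 0.05. The more serious risk is the within-arm reading, which would report a fall in pressure in place of a comparison of devices. The conclusion that the test is mis-specified rests on the wording and the design and needs none of the assumed figures.

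**What to change.** In Sections 11.2 and 11.3, replace the paired t-tests with a two-sided between-arm comparison of independent groups, at minimum an independent-samples t-test. Report the mean difference with its 95% CI and state the alpha. Since baseline is already collected, ANCOVA of the month-12 value on arm and baseline would be preferable, but it is optional. If within-arm tests of change are kept, label them descriptive.

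The cost is wording in two sections and no new data. There is one consequence: once the independent test is named, 40 per arm gives about 60% power for 1.5 mmHg at SD 3 (two-sided 0.05 assumed), not the 80% in Section 11.1. That section must be restated for the named test, which is a separate point.
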